3.3 Efficacy Variables

3.3.1 Potassium

Whole blood samples will be analyzed locally using POCT devices to generate K+ for the purposes of study inclusion, dose adjustments, and monitoring. Samples drawn at the same timepoints will be prepared and shipped to the central laboratory for analysis of sK+. In the event that hemolysis or other artifacts are suspected based on the reported POCT K+ result, the blood samples must be re-drawn to confirm the result and only the confirmatory sample result will be reported.

The primary endpoint will use the central laboratory sK+ measurement from Visit 7 if available and no use of rescue medication for hyperkalaemia has occurred. Missing measurements at Visit 7 will be imputed as follows:

(i) If Visit 7 central laboratory sK+ is missing

Visit 6 (or an unscheduled assessment which occurs between visits 6 and 7) central laboratory sK+ will be used in its place under the principle of last observation carried forward (LOCF). If multiple measurements are available, the closest measurement to the scheduled date of Visit 7 will be used.

(ii) If central laboratory sK+ is missing for Visits 6 and 7

sK+ will be replaced by POCT values adjusted to reflect the mean difference between POCT and sK+ values from all available (including screening, baseline and unscheduled visits) paired laboratory samples in both treatment groups. The mean difference will be estimated using a summary statistic of the difference in all pairs and will not adjust for baseline characteristics. If a Visit 7 POCT value is available the adjusted value for this will be used unless missing, in which case the adjusted Visit 6 POCT will be used. If an unscheduled POCT assessment which occurs between visits 6 and 7 is available, then the closest POCT assessment to the scheduled date of visit 7 will be used.

(iii) No sK+ or POCT K available for Visits 6 or 7

The subject will be classified as non-evaluable for primary and secondary efficacy endpoints which include sK+ measurements in their definition.

Normokalaemia is defined as $3.5 \le sK+ \le 5.0$ and hyperkalaemia is defined as sK+ > 5.0 where the sK+ value used will be the result of the imputation approach described above.

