4.2 Analysis methods

4.2.1 Subject Disposition and Analysis Sets Analyzed

Subject disposition will be listed and summarized by treatment group and overall. The number and percentage of subjects in the following categories will be summarized for subjects in the screened set:

- Screened;
- Did not enter open-label period (Screening failures) and associated reasons;
- Entered the open-label period and received treatment
- Entered the open-label period and did not receive treatment and associated reasons
- Randomized;
- Not randomized (Open-label period failure) and associated reasons;
- Randomized and received treatment;
- Randomized, did not receive treatment and associated reasons;
- Completed the study;
- Discontinued treatment and associated reasons (including use of rescue treatment);
- Terminated study and associated reasons;

The denominator used for percentages will be calculated as follows. The denominator for subjects who are screened or who did not enter the open-label period (and associated reasons) will be calculated using the number of screened subjects. The denominator for subjects who entered the open-label period and received treatment, who entered the open-label period and did not receive treatment (and associated reasons), randomized and not randomized (and associated reasons) will be calculated using the number of subjects who entered the open-label period. The remaining subject disposition categories will use the number of subjects who were randomized for the denominator. Categories will still be presented if 0 subjects satisfy the criteria.

The number of subjects in each of the analysis sets and the reasons for exclusion from each will be summarized for all screened subjects by treatment group and overall.

4.2.2 **Protocol Deviations**

All important protocol deviations (Section 2.2) leading to exclusion from the PPS will be listed and summarized by treatment group and overall for the FAS. Important protocol deviations will be further classified as either pandemic-related or excluding pandemic related important protocol deviations and will be summarized by treatment group and overall for the FAS.

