4.2.7.1 Primary Efficacy Analysis

The primary efficacy endpoint is the occurrence (yes/no) of patients having normal sK+ (between 3.5 and 5.0 mmol/L inclusive) on Day 29 (Visit 7) without rescue treatment for hyperkalemia at any point during the randomized phase in the SZC versus placebo arm. Patients with missing sK+ will have these imputed as described in section 3.3.1. The number and percentage of subjects who achieved a response (Yes, No, Non-evaluable) will be summarized by randomized treatment group in the FAS.

The occurrence will be compared between treatment groups in the FAS using a logistic regression model (excluding non-evaluable responses) including response as the dependent variable and randomized treatment as an independent factor, it will be tested using a two-sided

alpha = 0.05. The common odds ratio will be derived together with the two-sided 95% confidence interval.

Documentation will be provided to check the underlying assumptions for the logistic regression model. Standardized residuals will be presented in a scatter plot by alphanumerical subject ID. Subjects with standardized residuals > 3.0 will be listed. Influential observations on the regression coefficients will be detected by calculating Cook's D statistic (In SAS applied with proc reg with the plots=cooksd option) and presented in a diagnostic plot by alphanumerical subject ID. Subjects with Cook's D statistic > 4/sqrt(n) will be listed.

Estimand Attributes

In line with ICH E9 (R1) addendum, 5 attributes (treatment, population, endpoint, intercurrent events, and population-level summary) have been specified to translate the primary and key secondary efficacy objectives into treatment effects that are to be estimated (estimands).

Endpoint:

• Hyperkalaemia response, defined as an observed sK+ within 3.5-5.0 mEq/L at Day 29 (Visit 7)

Population:

• All subjects who achieve normokalemia at the end of the open-label correction phase, and are randomized

Treatment:

• SZC or Placebo. Patients with $sK+ \ge 6.0 \text{ mmol/L}$ will be managed with rescue therapy employing local standard of care.

Intercurrent Event Strategy:

- Discontinuation of treatment (Treatment policy strategy, i.e. regardless of the intercurrent event)
- Use of rescue therapy for hyperkalaemia at any point during the randomized placebocontrolled period (Composite variable strategy, i.e. considered to be non-response).

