- Use of rescue therapy for low bicarbonate at any point during the randomized placebocontrolled period (Treatment policy strategy, i.e. regardless of the intercurrent event).
- Death prior to Day 29 (Visit 7) (Composite variable strategy, i.e. considered to be non-response).
- Subject lost to follow-up prior to Day 29 (Visit 7) (Hypothetical strategy, i.e. assume response is not evaluable).
- Subject with no sK+ or POCT K measurement at visit 6 or visit 7 (Hypothetical strategy, i.e. assume response is not evaluable).

Population Level Summary:

• Odds ratio of the proportion of responders in the SZC treatment group compared to the placebo group.

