- Use of rescue therapy for low bicarbonate at any point during the randomized controlled period (While on treatment strategy, e.g. last observation carried forward).
- Death prior to Day 29 (Visit 7) (While on treatment strategy, e.g. last observation carried forward).
- POCT bicarbonate measurement unavailable for Visits 6 and 7 (Hypothetical strategy, assume response is missing).
- Subject lost to follow-up prior to Day 29 (Visit 7) (Hypothetical strategy, assume response is missing).

- Least squares mean estimate in the SZC treatment group compared to the placebo group.
- 2 Occurrence (yes/no) of patients having an increase in serum bicarbonate of ≥2 mmol/L on Day 29 (Visit 7) from baseline without need for rescue treatment for low bicarbonate in SZC versus placebo arm.

For secondary efficacy endpoints #2 - #7 the number and percentage of subjects with the endpoint (Yes, No, Non-evaluable) will be summarized by randomized treatment group in the FAS. Patients with missing sK+ or serum bicarbonate values at visit 7 will have these imputed as described in sections 3.3.1 and 3.3.1. The occurrence of each secondary efficacy endpoint will be compared between treatment groups in the FAS using a logistic regression model including the binary response endpoint as the dependent variable and randomized treatment as an independent factor, it will be formally tested using a two-sided alpha = 0.05 if the hierarchical testing strategy supports conducting a formal hypothesis test. The common odds ratio will be derived together with the two-sided 95% confidence interval.

For each secondary efficacy endpoint #2 - #7, documentation will be provided to check the underlying assumptions for the logistic regression model. Standardized residuals will be presented in a scatter plot by alphanumerical subject ID. Subjects with standardized residuals > 3.0 will be listed.

Endpoint:

• Serum bicarbonate response, defined as an increase from baseline in serum bicarbonate value ≥2 mmol/L at Day 29 (Visit 7)

Population:

• All subjects who achieve normokalemia at the end of the open-label correction phase, meet inclusion/exclusion criteria and are randomized

Treatment:

• SZC or Placebo. Patients with $sK+ \ge 6.0 \text{ mmol/L}$ will be managed with rescue therapy employing local standard of care.

- Discontinuation of treatment (Treatment policy strategy, i.e. regardless of the intercurrent event)

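### For the primary endpoint, a patient who was rescued for hyperkalaemia or died before Day 29 and has no Visit 6/7 potassium is both a non-responder and non-evaluable, and the SAP does not say which rule wins

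*SAP*

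**What the plan says.** The primary endpoint in SAP 4.2.7.1 is a normal potassium on Day 29 "without rescue treatment for hyperkalemia at any point during the randomized phase in the SZC versus placebo arm". The estimand list in that section then gives these rules:

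- Rescue: "Use of rescue therapy for hyperkalaemia at any point during the randomized placebocontrolled period (Composite variable strategy, i.e. considered to be non-response".
- Death: "Death prior to Day 29 (Visit 7) (Composite variable strategy, i.e. considered to be non-response".
- No late potassium: "Subject with no sK+ or POCT K measurement at visit 6 or visit 7 (Hypothetical strategy, i.e. assume response is not evaluable".

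SAP 3.3.1 rule (iii) repeats the last of these at the derivation level: "The subject will be classified as non-evaluable for primary and secondary efficacy endpoints which include sK+ measurements in their definition". It makes no exception for rescue or death. The primary comparison is a "logistic regression model (excluding non-evaluable responses").

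SAP 3.3.1 also says that the Visit 7 central laboratory value is used when it is available and no hyperkalaemia rescue has taken place. It does not say there what a rescued patient's outcome is.

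**The concern.** The composite strategy exists so that rescue or death settles the outcome without a Day 29 potassium. Rule (iii) and its matching estimand bullet settle it the other way for the same patient. Both stand in the same list, with no order between them. If the non-evaluable rule is applied first, decided failures leave the primary test, and the odds ratio no longer estimates what 4.2.7.1 says it estimates. The primary result is also the gate for all secondary tests under SAP 4.2.7. An unstated order would leave that choice open to whoever writes the derivation.

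**Working it through.** **Where the rules collide**

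| Patient | Composite rule (4.2.7.1) | Rule (iii) of 3.3.1 and last estimand bullet | In the model? |
|---|---|---|---|
| Dies on Day 10, no later sample | Non-response | Non-evaluable | Depends on order |
| Rescued in week 1, leaves, no Visit 6/7 potassium | Non-response | Non-evaluable | Depends on order |
| Rescued, Visit 6 or 7 potassium available | Non-response | Does not apply | Yes, as a failure |
| No rescue, alive, no Visit 6/7 potassium | Does not apply | Non-evaluable | No |

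Only the first two rows are in conflict. The Visit 6 analysis window opens on Day 19 (SAP 3.1, Table 1), so an earlier death always meets both rules. SAP 2.3 ends the randomized analysis period at rescue. If values taken after rescue were treated as outside that period, the third row could join the conflict; the SAP does not say.

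**Where the clash recurs**

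- Endpoints #2 to #6: death is non-response, but no Visit 6/7 value is not evaluable.
- Endpoint #1: death carries the last value forward, but the list also has "POCT bicarbonate measurement unavailable for Visits 6 and 7 (Hypothetical strategy, assume response is missing".
- Endpoint #7: the outcome is bicarbonate rescue itself, yet a rescued patient with no Visit 6/7 bicarbonate is not evaluable.
- Endpoints #4 and #6: no rule says that an observed failing component decides the outcome when the other component is missing.
- COVID-19 sensitivity analysis (4.2.7.2): the rescue and death bullets stand beside the same not-evaluable bullet, again unranked.

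**The plan's own figure.** SAP 1.3 sizes the trial on the ≥3 mmol/L bicarbonate response, 0.175 v 0.39, two-sided 0.05, 80% power. With pooled variance and mean proportion 0.2825:

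n = [1.96√(2 × 0.2825 × 0.7175) + 0.8416√(0.39 × 0.61 + 0.175 × 0.825)]² / 0.215² = 67.6, so 68 per arm. This agrees with the SAP. It gives no response rates for the primary endpoint, so everything below is illustration.

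**Effect on the odds ratio.** Assume response of 80% on SZC and 45% on placebo, so failures are 20% and 55%. Let d be the percentage of an arm that is in conflict. All are failures, so dropping them changes only the failure counts:

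OR after = [80/(20 − d_SZC)] / [45/(55 − d_placebo)]

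Power uses the pooled-variance normal approximation with the reduced arm sizes: Φ[(difference − 1.96·s0)/s1], where s0 is the pooled and s1 the unpooled standard error.

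| Dropped, SZC v placebo | Rates left | OR | s0, s1 at 68 per arm | Power |
|---|---|---|---|---|
| None (non-response) | 80.0% v 45.0% | 4.89 | 0.0830, 0.0774 | 99% |
| 2% v 15% | 81.6% v 52.9% | 3.95 | 0.0836, 0.0810 | 94% |
| 2% v 5% | 81.6% v 47.4% | 4.94 | 0.0834, 0.0782 | 99% |
| 5% v 5% | 84.2% v 47.4% | 5.93 | 0.0835, 0.0769 | over 99% |

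Worked case, 2% v 15%: OR = (80/18)/(45/40) = 4.444/1.125 = 3.95. Power = Φ[(0.2869 − 1.96 × 0.0836)/0.0810] = Φ(1.52) = 94%.

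The direction depends on the share of each arm's failures that is removed, not on the raw count. At 2% v 5% the shares are 2/20 = 10% and 5/55 = 9.1%, so the OR rises slightly although more placebo patients are dropped. At 2% v 15% they are 10% and 27.3%, so it falls.

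**A smaller assumed effect.** Take 68 per arm with 48 v 34 responders (Wald test on the log odds ratio, as in a treatment-only logistic model):

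- All conflicts as failures: (48/20)/(34/34) = 2.40, p = 0.015.
- Drop 3 SZC and 10 placebo: (48/17)/(34/24) = 1.99, p = 0.076.
- Drop 7 and 7: (48/13)/(34/27) = 2.93, p = 0.008.

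So the order can move the primary result across 0.05, in an assumed case.

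**The case against.** The strongest reply is that the composite intent is clear. The endpoint itself requires no rescue, 3.3.1 mentions rescue before any missing-data rule, and the composite bullets come first in 4.2.7.1. A careful analyst would probably let them win. That weakens the practical risk for rescue but does not remove the contradiction: the condition in 3.3.1 only limits when the Visit 7 value is used, it is silent on death, and listing order is not a stated precedence.

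A reader might infer that the SAP deletes known failures, mainly from placebo, and so understates the treatment effect. The documents do not support that. Deletion follows only if the non-evaluable rule is applied first. More hyperkalaemia rescue on placebo is plausible if SZC works, but no rates by arm are given, and nothing suggests that deaths would fall mostly on placebo. Balanced losses raise the odds ratio in the examples above.

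A reader might also take the disposition line in SAP 4.2.1, "Discontinued treatment and associated reasons (including use of rescue treatment"), as showing that the overlap is expected. It concerns stopping treatment. Leaving the study is a separate line there, and stopping treatment is handled by a treatment policy strategy, under which measurement should continue. How many patients would lack a late potassium is unknown.

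For endpoint #1, SAP 4.2.7.3 already assigns the last value before low-bicarbonate rescue, with no Visit 6 limit. Only death is left open there, although the missing-value bullet still lacks an exemption for either case.

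**Conclusion.** The point holds as an unresolved contradiction in the primary endpoint. Applied literally, rule (iii) removes patients whose failure another rule has already decided, so the text is wrong as written and not merely brief. It affects only patients with rescue or death and no usable potassium from Visit 6 onward.

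Its size and direction cannot be fixed from the SAP. Under the assumed 80% v 45% response, the odds ratio of 4.89 becomes anything from 3.95 to 5.93 across the three loss patterns shown, and power at 68 per arm falls to 94% at worst among them. With the smaller assumed effect, significance can change. The study stopped early and the SAP gives no final number. At an assumed 40 or 20 per arm, the 2% v 15% case lowers power from 91% to 76% or from 64% to 46%.

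**What to change.** State one derivation order in SAP 3.3.1, 3.3.2 and every estimand list, including the COVID-19 sensitivity analysis:

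1. Classify first any death before Day 29 and any rescue that the endpoint definition rules out. Both are non-response for the primary endpoint and for #2 to #6. For #2 to #6 this replaces the while-on-treatment (last observation carried forward) bullets for those rescues, which contradict endpoint definitions that require no rescue. For #7, an observed rescue is an event.
2. For #4 and #6, an observed failing component is non-response, whatever is missing on the other.
3. Then apply the Visit 7, Visit 6 and substitute-assay rules.
4. Classify as non-evaluable only when none of these steps decides the outcome.

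For #1, keep the existing sentence on low-bicarbonate rescue. Add that after death the last randomized-period value is used even if it precedes Visit 6, and exempt both cases from the missing-value bullet.

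The cost is a few lines of SAP text and the order of steps in the endpoint derivation, settled before database lock. No new data are needed.

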3.3.2 Bicarbonate

Whole blood samples will be analyzed locally using POCT devices to generate POCT serum bicarbonate measurements (TCO2). The secondary endpoints will use the POCT serum bicarbonate measurement from Visit 7 if available. For the first secondary endpoint analysing the mean change in serum bicarbonate from baseline, missing measurements at visit 7 will be imputed as follows:

(i) If Visit 7 POCT serum bicarbonate measurements are unavailable

Visit 6 (or an unscheduled assessment which occurs between visits 6 and 7) POCT serum bicarbonate will be used in its place under the principle of LOCF. If multiple measurements are available, the closest measurement to the scheduled date of Visit 7 will be used.

As a sensitivity analysis for the secondary endpoint #1, and as standard imputation approach for the other secondary endpoints which include serum bicarbonate measurements, the additional imputation rule will be applied:

(ii) If POCT bicarbonate is missing for Visits 6 and 7

POCT bicarbonate will be replaced by central laboratory bicarbonate values adjusted to reflect the mean difference between POCT and central laboratory bicarbonate values from all available (including screening, baseline and unscheduled visits) paired laboratory samples in both treatment groups. The mean difference will be estimated using a summary statistic of the difference in all pairs and will not adjust for baseline characteristics. If a visit 7 central laboratory value is available the adjusted value for this will be used unless missing, in which case the adjusted Visit 6 central laboratory measurement will be used. If an unscheduled central laboratory assessment which occurs between visits 6 and 7 is available, then the closest available assessment to the scheduled date of visit 7 will be used.

(iii) No POCT or central laboratory bicarbonate available for Visits 6 or 7

The subject will be classified as non-evaluable for secondary efficacy endpoints which include serum bicarbonate measurements in their definition.

Thresholds for the change from baseline for the imputed serum bicarbonate value described above of $\geq 2 \text{ mmol/L}$ and $\geq 3 \text{ mmol/L}$ will be calculated and an absolute value of $\geq 22 \text{ mmol/L}$ or <15 mmol/L.

3.3.3 Additional serum measurements

Whole blood samples will be analyzed locally using POCT devices to generate POCT creatinine and anion gap measurements. If POCT does not generate anion gap values, then anion gap will be derived using the formula:

Anion gap (mEq/L) = sodium (mEq/L) - (chloride (mEq/L) + bicarbonate (mEq/L))

Where sodium, chloride and bicarbonate are measured at the same visits as discussed below.

3.3.4 Urine analysis

When possible, first morning void spot urine will be collected at visits 1, 3-8 and in the event of early withdrawal. Urinary albumin, ammonium, citrate, pH, and creatinine will be measured at the central laboratory. Urine anion gap will be calculated based on sodium, potassium, and chloride ions using the formulate provided in section 3.3.3. Urine albumin-to-creatinine-ratio (UACR) will be calculated based on the measured urinary albumin and creatinine. Ammonium-to-creatinine ratio will be calculated based on the measured urinary ammonium and creatinine. The urine anion gap, UACR and ammonium-to-creatinine ratio will be calculated by the central laboratory.

If visit 7 central laboratory measurements are unavailable, then visit 6 values will be used under the principle of LOCF.

3.4 Safety Variables

3.4.1 Exposure and dose interruptions

Exposure (i.e. duration of treatment) will be defined as follows:

Total (or intended) exposure of study treatment

• Total (or intended) exposure = min (last dose date where dose > 0 [units], date of death, date of discontinuation) – first dose date + 1

Actual exposure of study treatment

• Actual exposure = total (or intended) exposure – total duration of dose interruptions, where intended exposure will be calculated as above and a dose interruption is defined as any length of time where the subject has not taken any of the planned daily dose. The duration of each dose interruption will be calculated as interruption stop date – interruption start date + 1.

The actual exposure calculation makes no adjustment for any dose reduction that may have occurred.

3.4.2 Adverse Events

Adverse events (AEs) and Serious adverse events (SAEs) will be collected from start of the open-label correction phase, throughout the treatment period and including during the follow-up period. In addition, SAEs will be recorded from the time of signing the informed consent form and will continue throughout the clinical study until the end of any follow-up prior; this applies even if the subject has not received any study treatment (as per the SOP: Reporting of Individual Safety Events in Clinical Studies). SAEs which occur after the end of the clinical study but with a suspected causal relationship to the IP will be reported by the investigator but will not be included in summary tables and listings.

A treatment emergent AE (TEAE) will be defined as an AE with the start date on or after the first dose date and up to (and including) 7 days after the last dose date or an AE which starts prior to first dose of IP (i.e. before study day 1) which subsequently worsen in severity on or after the date of first dose of IP and up to and including 7 days following the date of last dose of study medication. AEs which occur more than 7 days after the last dose date will only be listed. Similarly, the number of patients experiencing SAEs, AEs that led to withdrawal, AEs that led to death and treatment related AEs, and number of such events, will be summarized by treatment group.

AEs will be further categorized as either occurring during the open-label period, if the start date is on or after the first dose date during the open-label correction period and prior to the date of the first dose of treatment during the randomized placebo-controlled period, or occurring during the randomized placebo-controlled period if the start date is on or after the date of the first dose of treatment during the randomized placebo-controlled period.

The Medical Dictionary for Regulatory Activities (MedDRA) (using the latest or current MedDRA version) will be used to classify AEs system organ class (SOC) and preferred term (PT).

If the relationship to treatment is missing, then the AE will be considered as possibly related to treatment.

Other significant adverse events

An overview of edema-related events (grouped terms include preferred terms of edema, edema peripheral, generalized edema, fluid overload, fluid retention, hypervolemia, localized edema, and peripheral swelling)and instances of sK+ <3.5 will be presented.

Deaths

All AEs leading to death will be collected until the end of the study.

Laboratory Data

Deterioration as compared to baseline in protocol-mandated laboratory values will only be reported as AEs if they fulfil any of the SAE criteria, are the reason for discontinuation of treatment with the IP or are considered to be clinically relevant as judged by the investigator (which may include but not limited to consideration as to whether treatment or non-planned visits were required or other action was taken with the study treatment, e.g., dose adjustment or drug interruption).

Vital Signs Data

Deterioration as compared to baseline in protocol-mandated vital signs should therefore only be reported as AEs if they fulfil any of the SAE criteria, are the reason for discontinuation of treatment with the IP or are considered to be clinically relevant as judged by the investigator (which may include but not limited to consideration as to whether treatment or non-planned visits were required or other action was taken with the study treatment, eg, dose adjustment or drug interruption).

